10.9 Other Topics

Not applicable.

11 ADVERSE EVENTS

11.1 Monitoring, Recording and Reporting of Adverse Events

An adverse event (AE) is any noxious, unintended, or untoward medical occurrence that may appear or worsen in a subject during the course of a study. It may be a new intercurrent illness, a worsening concomitant illness, an injury, or any concomitant impairment of the subject's health, including laboratory test values (as specified by the criteria in Section 11.3), regardless of etiology. Any worsening (ie, any clinically significant adverse change in the frequency or intensity of a pre-existing condition) should be considered an AE. A diagnosis or syndrome should be recorded on the AE page of the CRF rather than the individual signs or symptoms of the diagnosis or syndrome.

An overdose, accidental or intentional, whether or not it is associated with an AE, or abuse, withdrawal, sensitivity or toxicity to an investigational product should be reported as an AE. If an overdose is associated with an AE, the overdose and adverse event should be reported as separate terms. See Section 8.2.4.1 for more details.

All subjects will be monitored for AEs during the study. Assessments may include monitoring of any or all of the following parameters: the subject's clinical symptoms, laboratory, pathological, radiological or surgical findings, physical examination findings, or findings from other tests and/or procedures.

All AEs will be recorded by the investigator from the time the subject signs informed consent until 28 days after the last dose of IP and those SAEs made known to the investigator at any time thereafter that are suspected of being related to IP. AEs and serious adverse events (SAEs) will be recorded on the AE page of the CRF and in the subject's source documents. All SAEs must be reported to Celgene Drug Safety within 24 hours of the investigator's knowledge of the event by facsimile, or other appropriate method, using the SAE Report Form, or approved equivalent form. Note that second primary malignancies will be monitored as events of interest and must be reported as serious adverse events regardless of the treatment arm the subject is in (see Section 11.5).

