2.2 Secondary Objectives

The secondary objectives of the study are:

- To compare the safety of lenalidomide plus rituximab combination maintenance therapy (for 18 cycles) followed by optional lenalidomide single-agent maintenance (to progression) versus rituximab single-agent maintenance (for 18 cycles) after 12 cycles of induction therapy with lenalidomide plus rituximab.
- To compare other parameters of efficacy (OS, IOR, ORR, CRR, DOR, DOCR, TTNLT, TTHT) of lenalidomide plus rituximab combination maintenance therapy (for 18 cycles) followed by optional lenalidomide single-agent maintenance (to progression) versus rituximab single-agent maintenance (for 18 cycles) after 12 cycles of induction therapy with lenalidomide plus rituximab.

All efficacy assessments will be assessed using a modification of the IWG 1999 criteria (Cheson, 1999) to allow the inclusion of extranodal disease as measurable disease.

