8 DESCRIPTION OF STUDY TREATMENTS

8.1 Description of Investigational Product(s)

Investigational products in this study are lenalidomide and rituximab.

Celgene Corporation will supply lenalidomide 2.5 mg, 5 mg, 10 mg, 15 mg, and 20 mg capsules for oral administration. Subjects will receive treatment with lenalidomide for 21 days per Cycle.

Study drug will be packaged in bottles containing study capsules for days 1 - 21 of every 28 day Cycle.

Commercially available intravenous (IV) formulation of rituximab may be used.

In Germany, Celgene Corporation will supply both lenalidomide capsules and rituximab intravenous formulation as investigational products.

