8.2 Treatment Administration and Schedule

Eligible subjects entering the Induction Treatment Phase will be enrolled using an Interactive Voice Response System (IVRS). Subjects entering the Maintenance Phase will be randomized using the IVRS into one of two arms (experimental or control) in a 1:1 ratio. Randomization will be stratified as described in Section 8.3. Subjects randomized under previous protocol (version 16 January 2014) who achieve a response of SD or better at the end of the Induction Treatment Period will remain in their originally assigned arm of maintenance therapy.

Study Treatments, please see Sections 8.2.1 and 8.2.2 for details

• Induction Period (12 Cycles)

Lenalidomide 20 mg (10 mg if creatinine clearance \geq 30 mL/min but < 60 mL/min) once daily on Days 1 to 21 of every 28-day Cycle for Cycles 1 to 12 **AND** rituximab 375 mg/m² every week in Cycle 1 (Days 1, 8, 15, and 22) and Day 1 of every 28-day Cycle for Cycles 3, 5, 7, 9, and 11

Followed by Maintenance Period

- Arm A (Experimental arm): Lenalidomide + rituximab (Maintenance) followed by optional lenalidomide (Maintenance)
 - Maintenance Period (18 Cycles)

Lenalidomide 10 mg once daily on Days 1 to 21 of every 28-day Cycle for Cycles 13 to 30 AND rituximab 375 mg/m2 on Day 1 of every 28-day Cycle for Cycles 13, 15, 17, 19, 21, 23, 25, 27, and 29

Followed by

- Optional Maintenance Period (up to PD)

Lenalidomide 10 mg once daily on Days 1 to 21 of every 28-day Cycle up to PD. This treatment will be at the discretion of the subject and the investigator.

VERSUS

• Arm B (Control arm): Rituximab (Maintenance)

Maintenance Period (18 Cycles)
 Rituximab 375 mg/m2 on Day 1 of every 28-day Cycle for Cycles 13, 15, 17, 19, 21, 23, 25, 27, and 29

Induction treatment must begin no later than 1 week after enrollment in IVRS to receive induction therapy. The Treatment Period for each subject starts with first intake of study drug, which is defined as Day 1 of Cycle 1.

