10.7 Safety Analysis

Safety analyses will be based on all subjects in the safety population, and will be analyzed by the induction period, maintenance period, and follow-up period.

Study drug exposure will be summarized, including duration of study drug, total dose taken, and dose reductions.

Adverse events, vital sign measurements, clinical laboratory measurements, and concomitant medications will be summarized.

AEs will be coded according to Medical Dictionary for Drug Regulatory Activities (MedDRA) and classified using the National Cancer Institute Common Terminology Criteria for Adverse Events (CTCAE version 4.03, except for tumor flare, which will be assessed using version 3.0). The incidence rates of AEs will be tabulated by system organ class and preferred term. The incidence of AEs will also be tabulated by severity within each system organ class and preferred term. The most severe grade of each preferred term for a subject will be utilized for summaries of AEs by NCI CTCAE grade.

Subsets of AEs to be summarized include AEs, suspected treatment-related AEs, and AEs that result in withdrawal of investigational product.

AEs of interest include SPM, VTE, ATE, TLS, and TFR. All AEs with corresponding attributes will be displayed in a by-subject listing. Adverse events leading to death or to discontinuation from treatment, events classified as CTCAE Grade 3 or higher, suspected treatment-related events, and SAEs will also be displayed in separate by-subject listings.

Laboratory data will be summarized according to the CTCAE severity grade.

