11.2.1 Seriousness

A serious adverse event (SAE) is any AE occurring at any dose that:

- Results in death;
- Is life-threatening (ie, in the opinion of the investigator, the subject is at immediate risk of death from the AE);
- Requires inpatient hospitalization or prolongation of existing hospitalization (hospitalization is defined as an inpatient admission, regardless of length of stay);
- Results in persistent or significant disability/incapacity (a substantial disruption of the subject's ability to conduct normal life functions);
- Is a congenital anomaly/birth defect;
- Constitutes an important medical event.

Important medical events are defined as those occurrences that may not be immediately life threatening or result in death, hospitalization, or disability, but may jeopardize the subject or require medical or surgical intervention to prevent one of the other outcomes listed above. Medical and scientific judgment should be exercised in deciding whether such an AE should be considered serious.

Second primary malignancies will be monitored as events of interest and must be reported as serious adverse events regardless of the treatment arm the subject is in (see Section 11.5). This includes any second primary malignancy, regardless of causal relationship to IP (study drug[s] or control), occurring at any time for the duration of the study, from the time of signing the ICD for 5 years from the date the last subject initiates induction therapy. Events of second primary malignancy are to be reported using the SAE report form and must be considered an "Important Medical Event" if no other seriousness criteria apply; these events must also be documented in the appropriate page(s) of the CRF and subject's source documents. Documentation on the diagnosis of the second primary malignancy must be provided at the time of reporting as a serious adverse event (e.g., any confirmatory histology or cytology results, X-rays, CT scans, etc.).

Events **not considered** to be SAEs are hospitalizations for:

- A standard procedure for protocol therapy administration. However, hospitalization or prolonged hospitalization for a complication of therapy administration will be reported as an SAE.
- Routine treatment or monitoring of the studied indication not associated with any deterioration in condition.

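### Lymphoma progression is not exempted from the AE definition, and because the AE window differs by arm, progressions enter the by-arm safety tables in a proportion that does not reflect how often each arm progresses

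*Combined protocol and SAP*

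**What the plan says.** Section 11.1 defines worsening broadly: "Any worsening (ie, any clinically significant adverse change in the frequency or intensity of a pre-existing condition) should be considered an AE". On timing it says: "All AEs will be recorded by the investigator from the time the subject signs informed consent until 28 days after the last dose of IP". Second primary malignancies and later SAEs suspected to be related to study drug are collected beyond that point. Section 8.1 adds: "Investigational products in this study are lenalidomide and rituximab", so a rituximab dose sets the window as much as a lenalidomide dose does.

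Section 11.2.1 lists hospitalisations that are not SAEs. One is: "Routine treatment or monitoring of the studied indication not associated with any deterioration in condition". Another covers elective care of a pre-existing condition, but only one unrelated to the studied indication. Neither releases a deterioration of the lymphoma.

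Section 10.7 reports AE incidence by system organ class and preferred term, by study period, and says: "Subsets of AEs to be summarized include AEs, suspected treatment-related AEs, and AEs that result in withdrawal of investigational product". It names no progression terms to be left out.

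Section 8.2 gives both arms the same maintenance antibody schedule: "rituximab 375 mg/m2 on Day 1 of every 28-day Cycle for Cycles 13, 15, 17, 19, 21, 23, 25, 27, and 29". Arm A also takes lenalidomide on Days 1 to 21 of Cycles 13 to 30, and may then continue it alone until progression. That last phase is optional. Section 2.2 sets as a secondary objective: "To compare the safety of lenalidomide plus rituximab combination maintenance therapy" against rituximab alone.

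**The concern.** Every subject enters with lymphoma, so on the literal text its clinically significant progression is an AE. The event that defines efficacy failure is then also counted as a safety event. That alone would blur the safety tables. The larger difficulty is that the collection window is tied to the last dose, and the last dose falls at different times in the two arms. Arm B has no study drug after Cycle 29 Day 1, whereas some Arm A subjects may be dosed until they progress.

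At stake is the between-arm safety comparison. If Arm A's progressions are captured more completely, its AE incidence carries a larger share of efficacy failures than Arm B's, even when Arm A progresses less often. Section 10.8 also lets the DMC recommend stopping on the safety profile.

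**Working it through.** **1. Design hazard ratio.** The value is redacted, but Section 10.3 describes 0.533 as 20% better than assumed, so HR = 0.533/0.8 = 0.666. Check by the Schoenfeld formula: events = 4 × (1.960 + 0.842)² / (ln 0.666)² = 191, as stated. Power at 114 events is 58.2% (stated 57.9%).

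**2. When the window closes.** Count days from Cycle 13 Day 1 as day 0.

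- Arm B: Cycle 29 Day 1 = 16 × 28 = day 448; plus 28 = **day 476** (15.6 months).
- Arm A without the optional phase: Cycle 30 Day 21 = 17 × 28 + 20 = day 496; plus 28 = **day 524** (17.2 months).
- Arm A with the optional phase: open until 28 days after lenalidomide stops, so possibly to progression.

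The scan after Cycle 30 is due at 18 × 28 = day 504 (490 to 518 with the ±2-week allowance). It lies outside Arm B's window and inside that of an Arm A subject who completed the 18 cycles.

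**3. Dosing interval.** Maintenance rituximab falls on days 0, 56, 112, and so on to 448. Section 6.3 scans fall due on days 168, 336 and 504, and the first two are rituximab days. A progression found on such a scan before that day's infusion is 56 days after the previous dose, or 42 days if the scan is 14 days early. Counted strictly from the actual last dose, it is outside 28 days. Lenalidomide gaps are about 7 days, so this does not arise for an Arm A subject on lenalidomide.

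**4. Closed-form count, treating Arm B's window as open to day 476.** Take 314/2 = 157 per arm and exponential PFS. The control median is assumed to be 65 months, the value that gives 114 events at month 105 with uniform entry to maintenance over months 12 to 75 and 5% annual dropout. Then the control hazard is ln 2/65 = 0.01066 per month, and 0.666 times that is 0.00710 for Arm A.

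- Arm B: 157 × (1 − e^(−0.01066 × 15.64)) = 24.1.
- Arm A, no optional uptake: 157 × (1 − e^(−0.00710 × 17.22)) = 18.1.
- Arm A, everyone continuing to progression: 54.7, that is, 36.6 more.

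With uptake u, Arm A has 18.1 + 36.6u. The A/B ratio is 0.75 at u = 0, 36.4/24.1 = 1.51 at 50% and 54.7/24.1 = 2.27 at 100%. The arms are equal at u = 6.0/36.6 = 16%. With control medians of 18 to 84 months and follow-up of 36 to 60 months, break-even uptake is 16% to 39%. These counts use all PFS events and ignore stopping lenalidomide for other reasons. With 30% per year stopping it, Arm A's share at full uptake is 55% to 62%.

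**5. Simulation with detection at scans.** Inputs: 157 per arm, HR 0.667, control median 66 months, cut-off at month 105, 5% annual dropout. Assumed: 90% of events are progressions, 20% to 50% are found clinically between scans, toxicity stops treatment in 20% (A) and 10% (B) per year, and 20% to 30% per year stop optional lenalidomide. Detected progressions are about 41 or 42 in Arm A and 55 to 57 in Arm B, a ratio of about 0.74. Those captured as AEs:

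| Reading of the window | Optional uptake | Arm A | Arm B | A/B |
|---|---|---|---|---|
| Open during ongoing maintenance | 0–10% | – | – | 0.8–0.9 |
| Open during ongoing maintenance | 30–70% | 16–21 | 15–17 | 1.0–1.4 |
| Strict 28 days, scans spread ±14 days | 0% | about 12 | about 7 | 1.6–1.7 |
| Strict 28 days, scans spread ±14 days | 30–70% | 16–23 | 7–9 | 1.9–3.0 |
| Strict 28 days, all scans on or after due date | 0% | – | – | 0.97–1.13 |
| Strict 28 days, all scans on or after due date | 30–70% | – | – | 1.2–1.9 |

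The 1.4 on the open reading occurs only near 70% uptake; most results lie between 0.8 and 1.2. As a share of 157 subjects, 16–23 is 10–15%, 15–17 is 10–11%, and 7–9 is 4–6%. Per person-year in the window, A/B is 0.74 to 0.81 on the open reading and about 1.4 to 1.6 on the strict one.

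**The case against.** The strongest reply concerns the strict reading. When a maintenance scan shows progression in Arm B, the subject is still on protocol treatment and attending Day 1 visits, and nobody yet knows that the previous infusion was the last. An investigator would probably record the event. This stands, and it is why both readings are shown; most of the reversal of direction comes from the strict one.

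A reader might infer that progressions enter mainly in Arm A because only Arm A is treated to progression. The documents do not support that. The single-agent phase is optional and its uptake is not given. Within the 18 maintenance cycles both arms are treated until progression. With no uptake and an open window, Arm A supplies fewer captured progressions than Arm B. Progressions during the common induction belong to neither arm.

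A reader might also infer that fatal and AE-withdrawal figures are inflated in Arm A. Section 12.1 lists progression and adverse events as separate reasons for stopping treatment, and deaths long after progression fall outside both windows. No effect on these figures has been shown. Nor can it be said that exposure adjustment never helps: on the open reading it restores the expected direction.

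It can further be said that Section 11.1 requires a clinically significant change, so not every radiological progression need be recorded, and that Section 10.7 is descriptive. Both points stand; they make the counts above upper limits and leave the primary analysis untouched. The protocol also refers to a Statistical Analysis Plan, and no separate plan is in the text reviewed. If progression terms are handled there, Section 10.7 should point to it.

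**Conclusion.** The point holds in this form. No sentence in Sections 10.7, 11 or 12 exempts progression of the study lymphoma, the SAE exclusions point the same way, and the collection window is unequal between arms by construction. A detected-progression ratio of about 0.74 becomes roughly 0.8 to 1.2 (1.4 at the highest uptake tried) or about 1.0 to 3.0 among progressions captured as AEs, depending on how the window is read. In nearly every case Arm A's progressions are over-represented relative to their true frequency. Whether they outnumber Arm B's is conditional.

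The size rests on constant hazards, a design HR recovered from the 0.533 figure, assumed medians because the plan's are redacted, and assumed uptake, stopping and detection rates. The day-476 and day-524 limits and the 56-day interval come directly from the schedule. This is a worthwhile, cheap improvement to a stated secondary comparison and does not threaten the primary result.

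**What to change.** In Section 10.7, state that the by-arm maintenance summaries of AEs, Grade 3 or higher AEs and SAEs will be presented excluding preferred terms that denote progression of the lymphoma under study. Fix the list of terms before database lock, show the excluded terms by arm in one supplementary table, and retain the all-inclusive tables.

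Leave AE and SAE recording and reporting as they are: changing the Section 11.1 rule at Amendment 5 would mix two conventions in one database. Keep tumour flare and other sign or symptom terms in the main tables, because Section 6.2.11 warns that flare can be mistaken for progression and a broader exclusion could hide it.

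The cost is one extra set of tables and a review of the reported terms. No new data are needed.

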11.2 Evaluation of Adverse Events

A qualified investigator will evaluate all adverse events as to:

11.2.1 Seriousness

A serious adverse event (SAE) is any AE occurring at any dose that:

- Results in death;
- Is life-threatening (ie, in the opinion of the investigator, the subject is at immediate risk of death from the AE);
- Requires inpatient hospitalization or prolongation of existing hospitalization (hospitalization is defined as an inpatient admission, regardless of length of stay);
- Results in persistent or significant disability/incapacity (a substantial disruption of the subject's ability to conduct normal life functions);
- Is a congenital anomaly/birth defect;
- Constitutes an important medical event.

Important medical events are defined as those occurrences that may not be immediately life threatening or result in death, hospitalization, or disability, but may jeopardize the subject or require medical or surgical intervention to prevent one of the other outcomes listed above. Medical and scientific judgment should be exercised in deciding whether such an AE should be considered serious.

Second primary malignancies will be monitored as events of interest and must be reported as serious adverse events regardless of the treatment arm the subject is in (see Section 11.5). This includes any second primary malignancy, regardless of causal relationship to IP (study drug[s] or control), occurring at any time for the duration of the study, from the time of signing the ICD for 5 years from the date the last subject initiates induction therapy. Events of second primary malignancy are to be reported using the SAE report form and must be considered an "Important Medical Event" if no other seriousness criteria apply; these events must also be documented in the appropriate page(s) of the CRF and subject's source documents. Documentation on the diagnosis of the second primary malignancy must be provided at the time of reporting as a serious adverse event (e.g., any confirmatory histology or cytology results, X-rays, CT scans, etc.).

Events **not considered** to be SAEs are hospitalizations for:

- A standard procedure for protocol therapy administration. However, hospitalization or prolonged hospitalization for a complication of therapy administration will be reported as an SAE.
- Routine treatment or monitoring of the studied indication not associated with any deterioration in condition.
- The administration of blood or platelet transfusion as routine treatment of studied indication. However, hospitalization or prolonged hospitalization for a complication of such transfusion remains a reportable SAE.
- A procedure for protocol/disease-related investigations (e.g., surgery, scans, endoscopy, sampling for laboratory tests, bone marrow sampling). However, hospitalization or prolonged hospitalization for a complication of such procedures remains a reportable SAE.
- Hospitalization or prolongation of hospitalization for technical, practical, or social reasons, in absence of an AE.
- A procedure that is planned (ie, planned prior to starting of treatment on study); must be documented in the source document and the CRF. Hospitalization or prolonged hospitalization for a complication remains a reportable SAE.
- An elective treatment of or an elective procedure for a pre-existing condition unrelated to the studied indication, which has not worsened from baseline.
- Emergency outpatient treatment or observation that does not result in admission, unless fulfilling other seriousness criteria above.

If an AE is considered serious, both the AE page/screen of the CRF and the SAE Report Form must be completed.

For each SAE, the investigator will provide information on severity, start and stop dates, relationship to IP, action taken regarding IP, and outcome.

11.2.2 Severity / Intensity

For both AEs and SAEs, the investigator must assess the severity / intensity of the event.

The severity / intensity of AEs will be graded based upon the subject's symptoms according to the current active minor version of National Cancer Institute (NCI) Common Terminology Criteria for Adverse Events (CTCAE, Version 4.03). However, TFR will be graded using NCI CTCAE version 3.0. Severity grading for TLS should follow the Cairo-Bishop Grading System for TLS (Appendix D) rather than using the CTCAE v4.03.

AEs that are not defined in the NCI CTCAE should be evaluated for severity / intensity according to the following scale:

- Grade 1 = Mild transient or mild discomfort; no limitation in activity; no medical intervention/therapy required.
- Grade 2 = Moderate mild to moderate limitation in activity, some assistance may be needed; no or minimal medical intervention/therapy required.
- Grade 3 = Severe marked limitation in activity, some assistance usually required; medical intervention/therapy required, hospitalization is possible.
- Grade 4 = Life threatening extreme limitation in activity, significant assistance required; significant medical intervention/therapy required, hospitalization or hospice care probable.
- Grade 5 = Death the event results in death.

The term "severe" is often used to describe the intensity of a specific event (as in mild, moderate or severe myocardial infarction); the event itself, however, may be of relatively minor medical significance (such as severe headache). This criterion is *not* the same as "serious" which is based on subject/event *outcome* or *action* criteria associated with events that pose a threat to a subject's life or functioning.

Seriousness, not severity, serves as a guide for defining regulatory obligations.

